This is a pragmatic randomized controlled clinical trial that compares the effectiveness of a customized, home-based environmental intervention for improving asthma control (the "intervention") with enhanced clinic-based care (enhanced "usual care"). Each enrollee will be randomly assigned by a researcher not involved with patient care using a permuted block design with varying block size into one of two groups: (1) enhanced usual care, or (2) enhanced usual care plus home-based intervention. Based on known differences between younger and older adults, we will stratify the randomization by age (less than 55 and 55 or older years of age). Both arms would receive identical in-clinic care, including a tailored asthma self-management education program delivered using motivational interviewing techniques.

Inclusion Criteria:

The study population will be composed of African-American adults who are (1) 18 years of age or older; (2) have a diagnosis of poorly controlled asthma; (3) have a fixed address within Harris County, Texas with no intention of moving within the following 12 months; (4) have a working telephone number; and (5) are verbally fluent in English.

For purposes of this study, an individual with "poorly controlled asthma" (1) has been diagnosed by a physician as having asthma in the past and currently has asthma; and (2) fulfills one or more of the following criteria of poorly controlled asthma: * Has had one or more emergency department (ED), urgent care visits or hospitalizations for asthma in the preceding year; * Meets the definition of "very poorly controlled" asthma as defined by the National Asthma Education and Prevention Program, Third Expert Panel on the Diagnosis and Management of Asthma; this definition includes daily asthma symptoms, nighttime awakenings two or more times per week, extremely limited normal activity, and/or daily use of a short-acting beta agonist for symptom control; and/or * Has an Asthma Control Test score of 19 or lower.

Exclusion Criteria:

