# THE HOUSTON HOME-BASED INTEGRATED INTERVENTION TARGETING BETTER ASTHMA CONTROL (HIITBAC) FOR AFRICAN AMERICANS

#### Statistical Analysis Plan

### Revision Dated 9/9/2018

## Power and Sample Size

Power and sample size calculations were performed using the PS program of Dupont and Plummer. The study was initially designed to recruit 300 patients in total. Based on the literature and our previous experience with the targeted participant population, we estimated a 35% LTF rate, resulting in 97 patients per group at the end of the study.

The primary outcome measures were the ACT™ score, MiniAQLQ score, and self-reported ED visits. For the ACT™ score, assuming a standard deviation of 4, a sample size of 97 participants per group gave greater than 99% power to detect a minimal clinically important difference (MCID)—which has been determined to be 3 for the ACT™ score—at the significance level of 0.05 (2-sided) using an independent, two-sample t-test assuming equal variances. For the MiniAQLQ score, assuming a standard deviation of 0.6, a sample size of 97 participants per group provided roughly 99% power to detect a MCID—which has been determined to be 0.5 for the MiniAQLQ score—at a significance level of 0.05 (2-sided) using an independent, two-sample t-test assuming equal variances. For ED visits, assuming a standard deviation of 3 for the number of self-reported ED visits for asthma over the previous 12 months, a sample size of 97 per group provided about 90% power to detect a difference of 1.4 in annual ED visits between the two groups at the significance level of 0.05 (2-sided) using an independent, two-sample t-test assuming equal variances.

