### Randomization

We used a permutated block design with varying block sizes, stratified by age (less than 55 and 55 years or older) and sex, to randomize enrollees into either the clinic-only or home-visit group. The randomization program was written into our online HIITBAC CTMS. Randomization was done at the end of the baseline clinic visit. No one knew the randomization status until the baseline visit was completed. Subsequently, the clinical and home-visit teams were aware of the randomization status, which was needed to provide customized standard of care. The persons

making the mid-year phone calls were blinded to randomization status. No data analysis aside from data audits, validity checks and summary data for the Data Safety Monitoring Board was begun until the intervention and data collection were completed.

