#### Statistical Analysis

Summary statistics were calculated for the entire cohort, stratified by treatment group. Baseline demographics, clinical outcomes, and environmental exposures were summarized by means (standard deviations), medians (ranges), or frequencies (percentages). Baseline characteristics were compared between treatment groups using an independent two-sample t-test, Wilcoxon rank sum tests, chi-square tests, or Fisher's exact test. Baseline summary statistics were also compared between patients who completed the study (N=193) and those who did not (N=71). All hypothesis tests were two-sided and assessed at the 0.05 level of significance.

Primary Outcome Analyses. The primary outcome measures of interest for this study were the ACT™, MiniAQLQ, and ED visits in the previous 12 months at exit. The ACT™ score is the sum of the scores of the 5 items included in the questionnaire. If any of the five items was missing a response, then no score was computed. The MiniAQLQ scores were computed using two methods, per scoring recommendations. The MiniAQLQ was first computed as the average of the scores for the 15 items. If any of the 15 items was missing a response, then no score was calculated. Alternatively, the MiniAQLQ was also scored if 2 or fewer responses were missing by replacing the missing responses with the worst score (regression to the null). After replacement, the MiniAQLQ was then calculated as the average of the scores for the 15 items. The alternative MiniAQLQ was used as the primary measure for asthma quality of life. ED utilization was measured by the frequency of visits to an ED during the 12-month period prior to the exit visit.

The initial analysis of the outcome measures used an independent, two-sample, two-sided t-test, assuming equal variances, to compare the mean ACT™ scores, MiniAQLQ scores, and ED visits over the previous 12 months between treatment groups at study exit. The equal variance assumption was tested using the F test at the .05 level and, if rejected, Welch's t-test approximation was used as alternative analysis. Approximate normality was assessed by using histograms, box-plots, skewness, kurtosis, and the Shapiro-Wilks test. Departures from

normality were addressed by using nonparametric analytic methods or data transformation.

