In addition to the t-test, the Wilcoxon rank-sum test and Fisher's exact test were used to compare treatment groups for the ED visits outcome measure. The Wilcoxon rank-sum test was used to test for significant differences in the location of the distribution of ED visits between treatment groups. The outcome measure was also redefined as a binary outcome to compare the proportion of participants who had at least one visit to the ED by treatment group using the Fisher's exact test. Other outcome measures were similarly compared between treatment groups using t-tests, Wilcoxon rank-sum tests, chi-square tests, or Fisher's exact tests.

To assess between-group differences for the primary outcome measures, we calculated the raw mean difference (MD) for the continuous variables, ACT™ and MiniAQLQ; and the odds ratio (OR) for the binary variable, ED visits.

Exploratory Analyses. Data on ACT™, MiniAQLQ and ED visits were collected at baseline, and approximately 6 months and 12 months after enrollment. As an initial exploratory analyses of our primary outcome measures, we performed a repeated measures analysis using a general linear mixed model (LMM) for the continuous variables (ACT™ and MiniAQLQ) and a logistic regression using a generalized estimating equation (GEE) for categorical data (ED visits) to examine change over time. These models assume an intent-to-treat analysis. The LMM and GEE models include all available observations in the analyses and assume the data are missing at random, applying the restricted maximum likelihood estimation method. For the repeated measures analyses, we included time, study group, and the interaction between time and study group. The slopes between baseline and 6 months and 6 months and exit were calculated for each treatment group. The difference between treatment groups was compared at each time point. For the ACT™ and MiniAQLQ scores, the LMM was used to compute the difference in means and 95% confidence intervals (Cls) for effect size between the two treatment groups between baseline and exit. The logistic regression model was used to estimate the odds of having at least one ED visit in the 12-month period before exit compared with the 12-month period before baseline. The model was used to compute the odds ratio (OR) and 95% CIs for the effect size between the two treatment groups between baseline and exit.

We also performed exploratory analyses of potential predictor variables. Independent

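### The exploratory repeated-measures models give each arm its own baseline, so the only effect intervals the SAP names carry chance baseline differences and lose precision

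*SAP*

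**What the plan says.** Under Exploratory Analyses (SAP, Statistical Analysis) a linear mixed model (LMM) is fitted to ACT and MiniAQLQ and a logistic GEE to any ED visit. The terms are given as "we included time, study group, and the interaction between time and study group". With a free group term, each arm has its own baseline mean or log-odds.

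The LMM supplies a difference in means with a 95% CI for the baseline-to-exit effect. The GEE sets the odds of a visit in the year before exit against the odds in the year before baseline, and is then used to "compute the odds ratio (OR) and 95% CIs for the effect size between the two treatment groups between baseline and exit". No working correlation is named for the GEE. The arms are also compared at every visit, with no interval mentioned.

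The primary analysis compares the arms at exit only. It reports a raw mean difference and an odds ratio, again with no interval mentioned.

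On timing, the SAP's Randomization section says "Randomization was done at the end of the baseline clinic visit". Protocol F2 assigns the arm at enrolment but keeps it hidden until that visit ends. Either way, baseline was recorded before anyone knew the allocation.

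**The concern.** Because baseline precedes knowledge of allocation, the two arms have the same expected baseline. An observed gap is chance. A model that estimates a separate baseline for each arm and takes the effect as a difference in change subtracts that gap in full, and so adds its sampling error to the treatment effect. A model with one shared baseline uses the same data and does not pay this price.

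These models are exploratory, but they are the only place where the SAP names confidence intervals. They are therefore the intervals a reader would use to judge how large or small the effect could be. ED visits need particular attention. One entry criterion is "Has had one or more emergency department (ED), urgent care visits or hospitalizations for asthma in the preceding year", so the share with a baseline visit is probably raised, and a log-odds becomes noisier as the proportion moves away from one half.

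**Working it through.** **Inputs.**
- From the SAP: two-sided 0.05; 97 per group; SDs of 4 (ACT), 0.6 (MiniAQLQ) and 3 (ED visits); 193 completers and 71 non-completers.
- Assumed: an even split, so n0 = 264/2 = 132 per arm at baseline and n1 = 193/2 = 96.5 at exit; month-6 data ignored.
- Not in the documents, so shown over a range: the baseline-exit correlation (r for scores, phi for any ED visit) and the proportions with an ED visit.

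**The plan's own figures.** 300 × 0.65 / 2 = 97.5, given as 97. Power is Φ(δ/(SD√(2/97)) − 1.96):
- ED visits: Φ(3.25 − 1.96) = 0.901, matching the stated figure of about 90%.
- ACT: Φ(5.22 − 1.96) = 0.9994.
- MiniAQLQ: Φ(5.80 − 1.96) = 0.9999.

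These describe the exit t-test, not the contrast discussed here.

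**ACT and MiniAQLQ.** Variance of the between-arm contrast relative to the exit-only comparison, with equal variances over time and n1/n0 = 0.731:
- difference in change, separate baselines: (1 − r²) + 0.731(1 − r)²
- exit contrast, separate baselines: (1 − r²) + 0.731r²
- exit contrast, common baseline: 1 − r²

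| r | Change | Exit, separate baselines | Exit, common baseline | Variance cut, change to common |
|---|---|---|---|---|
| 0.3 | 1.27 | 0.98 | 0.91 | 28% |
| 0.5 | 0.93 | 0.93 | 0.75 | 20% |
| 0.7 | 0.58 | 0.87 | 0.51 | 11% |

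The cuts equal 39%, 24% and 13% more participants (1.268/0.91, 0.933/0.75, 0.576/0.51). At r = 0.5 the 95% half-width falls from 1.09 to 0.98 for ACT and from 0.164 to 0.147 for MiniAQLQ. The change contrast is less precise than the exit-only comparison only when r is below √0.731/(1 + √0.731) = 0.46.

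If the baseline SD is k times the exit SD, (1 − r)² becomes (k − r)². At k = 0.8 the cuts are 17%, 8% and 1%.

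**ED visits.** On the logit scale let v = 1/(p(1 − p)). Among completers the ratio of odds ratios has relative variance (v1 + v0 − 2·phi·√(v0·v1))/v1. It exceeds 1 when phi < 0.5√(p1q1/(p0q0)), where p0 and p1 are the baseline and exit proportions and q = 1 − p.
- Break-even phi is 0.40 for 50% falling to 20%, 0.50 for 60% to 40%, and 0.63 for 80% to 50%.
- At an assumed 60% to 40%, the relative SEs are:

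| phi | Change, completers | Change, all baselines kept | Common baseline |
|---|---|---|---|
| 0.2 | 1.26 | 1.20 | 0.98 |
| 0.3 | 1.18 | 1.14 | 0.95 |
| 0.4 | 1.10 | 1.07 | 0.92 |
| 0.5 | 1.00 | 1.00 | 0.87 |
| 0.6 | 0.89 | 0.92 | 0.80 |

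The last column is √(1 − phi²). Simulated GEE fits with 97 per arm gave change-to-exit SE ratios of 1.27, 1.13 and 0.99 at phi 0.2, 0.35 and 0.5.

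- Where visits fall from baseline to exit, the change interval is certain to be wider only if the baseline share without a visit is less than half the exit share. For 70% to 30%, the largest attainable phi is √(0.3 × 0.3/(0.7 × 0.7)) = 0.43, below the break-even of 0.50.

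**The case against.** The strongest reply is that the models are labelled exploratory and are meant to describe change over time, so a change contrast suits their purpose. The primary t-tests, rank-sum test and Fisher test do not depend on them, and nothing is biased. All of this stands, and it limits the weight of the point.

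A reader might infer that the ED interval must be wider than one that ignores baseline, or that these models always add noise. The documents support neither. They give no correlation and no ED proportions, and above break-even the ED change interval is the narrower one (0.89 to 0.92 at phi 0.6). Nor do they show that baseline ED use is near its ceiling: an ED visit is one component of one of three entry routes, beside very poorly controlled asthma and an ACT score of 19 or lower. For the scores, the change contrast beats the exit t-test once r exceeds 0.46. Entry on poor control may also narrow the baseline spread, which shrinks the gain.

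It can also be said that baseline is dealt with elsewhere: the visit-by-visit comparison yields an exit contrast, the predictor regressions adjust for baseline, and Protocol Section G plans adjustment if imbalance is found. None of these repairs the named intervals. The exit contrast with separate baselines has relative variance 0.93 at r = 0.5, against 0.75 with a common baseline. The predictor regressions are not presented as effect estimates. Adjustment triggered by observed imbalance is a different procedure.

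Finally, the SAP's wording of the contrast is not fully explicit. If the exit contrast was intended, the SAP should say so.

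**Conclusion.** The point holds as a matter of precision. On the natural reading, the only effect intervals the SAP names are for a difference in change with separate baselines. With equal variances over time this is less precise than a common-baseline analysis at every correlation below 1.

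For ACT and MiniAQLQ the avoidable variance is about 28%, 20% and 11% at r = 0.3, 0.5 and 0.7. This rests on an even split of the completer counts and equal variances, and falls to 17%, 8% and 1% if the baseline SD is 0.8 of the exit SD.

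For ED visits the comparison with an exit-only odds ratio is conditional: the change interval is wider below a correlation of roughly 0.4 to 0.6. A low correlation is plausible for a yes/no outcome over 12 months, but that is an assumption. The primary conclusions are not at risk. The change is worth making because it needs no new data.

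**What to change.** In both models:
- Constrain the arms to one baseline mean or log-odds by dropping the baseline group term. Keep time, and keep group-by-time at each later visit where the outcome was collected. Protocol F2 describes the month-6 call as covering ACT and healthcare use, not MiniAQLQ, so check which visits apply.
- For the GEE, state an exchangeable or unstructured working correlation with robust standard errors. Under independence, the common-baseline model simply returns the exit odds ratio and gains nothing.
- Report the exit group contrast with its 95% CI as the effect size, and leave baseline out of the visit-by-visit comparison of arms.

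The cost is one term per model and a few lines of SAP text. The SAP is dated 9/9/2018 and describes its analyses as already done. If the specified models have been run, show both sets of results and label the common-baseline one as added later. Giving intervals for the primary mean difference and odds ratio is a separate gap that this change does not close.

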linear regression models were used to explore the association between various demographic, clinical and housing baseline characteristics and the primary continuous outcome measures, ACT™ and MiniAQLQ, adjusting for study group and baseline scores. Predictor variables were selected for inclusion in the final multivariable linear regressions based on statistical significance (generally alpha = .05), frequency of missing observations, clinical relevance, and model fit statistics such as the R-squared value. Residual plots and diagnostics were used to assess linear regression model assumptions. Independent logistic regression was similarly used to assess the association between baseline demographic, clinical and housing characteristics and exit ED visits (yes/no), adjusting for study group and baseline ED visits. A multivariable logistic regression model was similarly constructed for key predictor variables of ED visits at exit.

In addition, we performed a number of post hoc subgroup analyses including (1) enrollees who completed all five home visits; (2) enrollees who did not change addresses during the intervention; and (3) enrollees who exited before Hurricane Harvey. We also examined the heterogeneity of treatment effect (HTE) by looking at the interactions between age and treatment group, and gender and treatment group. Interaction terms were assessed in linear regression models. All HTE analyses were post hoc and exploratory in nature.

Analyses were done using SAS 9.4 (Cary, NC) and Stata 15 (College Station, TX).

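### Exploratory predictor models: variables chosen partly by p<.05 and R-squared are refitted on the same completers, so their final p-values, intervals and R-squared are optimistic

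*SAP*

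**What the plan says.** The SAP (Statistical Analysis, Exploratory Analyses) introduces this work as follows: "We also performed exploratory analyses of potential predictor variables". Each of the "various demographic, clinical and housing baseline characteristics" is examined in its own linear model for ACT or MiniAQLQ, "adjusting for study group and baseline scores".

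Four criteria then decide which variables go forward. The SAP says: "Predictor variables were selected for inclusion in the final multivariable linear regressions based on statistical significance (generally alpha = .05), frequency of missing observations", and then "clinical relevance, and model fit statistics such as the R-squared value". No order or weight is given. For ED visits (yes/no) the SAP says: "A multivariable logistic regression model was similarly constructed for key predictor variables of ED visits at exit".

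The SAP counts 193 completers and 71 non-completers and tests everything two-sided at 0.05. The protocol (Section G, data analysis) says that p-values are not adjusted for multiple comparisons. Neither document lists or counts the candidates, or describes a hold-out sample, cross-validation, bootstrap or shrinkage.

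**The concern.** A variable that enters a model because its p-value was small in these patients will tend to look significant when refitted in the same patients. The second p-value is not independent confirmation, and an ordinary interval takes no account of the selection. The estimates that pass the threshold are also, on average, the ones that chance has pushed away from zero.

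Raw R-squared adds to this. On a fixed set of rows it cannot fall when a variable is added, so as a selection criterion it never counts against noise. If candidate models also lose different rows to missing data, their R-squared values are not comparable. The SAP does not say whether that happened.

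What is at stake is the reading of the final models. Protocol Section I says the team wants to turn the programme into a package for other communities after integrating lessons learned. Housing and clinical predictors with overstated effects could influence that work, although the protocol does not tie it to these models.

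**Working it through.** **Inputs.** From the SAP: n = 193 completers (missing items would lower this), a screen at two-sided .05, and adjustment for study group and baseline score. Assumed, because the documents are silent: K = 20, 30 or 40 independent candidates, and a baseline-exit correlation of 0.5. Only the significance criterion is modelled. The plan gives no performance figure for these models. Its power figures concern the primary t-tests and play no part here.

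**1. False selections if every candidate is null.** The expected number per outcome is K × 0.05, and the chance of at least one is 1 − 0.95^K.

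**2. Refit on the same patients.** Simulation of 1,500 trials per setting: screen each candidate, refit the survivors jointly, and compare with fitting all K candidates without selection.

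| K | K × 0.05 | 1 − 0.95^K | Selected nulls with p<.05 in refit | At least one false predictor, screen and refit | Same, all K fitted in full |
|---|---|---|---|---|---|
| 20 | 1.0 | 64% | 88% | 63% | 61% |
| 30 | 1.5 | 79% | 83% | 77% | 75% |
| 40 | 2.0 | 87% | 82% | 85% | 83% |

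Repeat runs put the fourth column at 81% to 88% overall. For a null variable the 95% interval covers the truth exactly when p ≥ .05, so coverage among selected nulls at K = 30 is about 1 − 0.84 = 16%. Over three outcomes the expected false selections are 3.0, 4.5 and 6.0.

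**3. Overstatement of a real effect.** Take a standardised slope of 0.10. Its SE is about s/√193, where s is the residual SD and √193 = 13.89. With d = 0.10/SE and critical value 1.973 (189 df), the mean selected estimate in SE units is d + φ(1.973 − d)/[1 − Φ(1.973 − d)].
- Total outcome SD 1, so s = √0.75 = 0.866: SE = 0.0623, d = 1.604, mean = 1.604 + 1.047 = 2.651. Ratio 2.651/1.604 = 1.65.
- Residual SD 1: SE = 0.0720, d = 1.389, mean = 1.389 + 1.203 = 2.592. Ratio 2.592/1.389 = 1.87.

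**4. If some candidates are real.** Simulated share of significant final-model predictors that are noise, with independent candidates:

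| Real predictors (partial r) | K=10 | K=20 | K=30 | K=50 |
|---|---|---|---|---|
| 2 (0.15 to 0.20) | 16–25% | 30–42% | 39–52% | 52–64% |
| 5 (0.15 to 0.30) | 2–7% | 7–18% | 11–27% | 17–40% |

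**5. Correlated candidates (pairwise 0.3).** With all candidates null, 41% (K = 20) and 31% (K = 30) of selected variables are again significant. With five real predictors at partial r 0.20 the figure is 3% to 4%, because null variables then enter as proxies and are tested beside the real ones. The noise share of significant predictors is still 14% to 24%.

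The logistic model for ED visits was not simulated. The same argument applies, without a figure.

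**The case against.** Several points on the other side stand.

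- The work is labelled exploratory, and the primary comparisons (t-tests, with Wilcoxon and Fisher tests for ED visits) do not use these models.
- Clinical relevance is one of the four criteria, R-squared is only an example of a fit statistic, and the .05 level applies only generally. A purely mechanical screen is therefore a simplification. But with no weights and no candidate list, clinical relevance cannot be relied on as a safeguard.
- The chance of at least one false predictor is mostly multiplicity. At K = 30 it is 77% with selection and 75% with all candidates fitted. Fitting a long list in full would not lower it; a short list would.
- The 81% to 88% is conditional on having passed the screen. Unconditionally, about 1.5 × 0.84/30 = 4.2% of null candidates end up significant. The high figure shows that a second p<.05 adds little evidence. It does not show that the overall error rate per candidate is inflated.

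A reader might go further and infer that most of the reported predictors are noise. The documents do not support that. It needs the number of candidates and the share that are real, and neither is given. In the settings above with at least two real predictors and independent candidates, the noise share runs from 2% to 64% and passes one half only with a large pool and few or weak real effects.

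**Conclusion.** The concern holds for the exploratory predictor models only. Their final p-values, intervals and R-squared do not carry their usual meaning for variables selected on the same data, and an exploratory label does not correct them. With 20 to 40 independent null candidates, about 1 to 2 false selections per outcome are expected and 81% to 88% of them would look significant again. A small real effect (0.10) would be overstated about 1.7- to 1.9-fold when selected, depending on how the outcome is scaled.

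These sizes rest on an assumed number of candidates, independence between them, and a screen by p-value alone. Correlation between candidates lowers the refit figure, sharply in some settings. The actual false-positive share cannot be determined from the documents. Nothing here bears on the treatment effect.

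**What to change.** - List every candidate tested for each outcome, with its number of missing values, and state how the four criteria were combined.
- Bootstrap the whole selection procedure on one common data set. Report how often each variable is selected and an optimism-corrected R-squared. Alternatively, fit a short, clinically chosen set in full, without screening on p-values.
- Replace raw R-squared with adjusted or optimism-corrected R-squared wherever fit guides selection.
- Do not present ordinary p-values or intervals for data-selected predictors as valid inference; mark them as descriptive.

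The SAP is dated 9/9/2018 and is written in the past tense with completer counts, so a list fixed without sight of the exit data may no longer be possible. The bootstrap route does not need one. A penalised model such as LASSO would also serve, but that is a matter of preference.

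The cost is a little more analysis of existing data and probably fewer significant predictors to report.
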